### 9.6.3. **Safety**

#### **Adverse Events**

#### AE'S OF Special Interest

The following AESI have been selected using the reference dataset

(arenv/arprod/respiratory/res\_safety/aesi/refdata) and sub setting on the relevant study medications (VI or FF) with an indication of COPD along with review by Global Clinical Safety Pharmacovigilance (GCSP):

Adrenal Suppression (Selected PTs)

Asthma/Bronchospasm (SMQ)

Cardiovascular effects including the following subgroups:

- Cardiac Arrhythmia (Selected SMQs)
- Cardiac failure (SMQ)
- Stroke (CNS system haemorrhages and cerebrovascular conditions SMQ)
- Hypertension (SMQ)
- Cardiac Ischaemia (Ischaemic heart disease SMQ)

Decreased Bone Mineral Density and associated Fractures (Selected PTs + Osteoporosis/Osteopenia SMQ)

Effects on potassium (Selected PTs)

Effects on glucose (Hyperglycaemia/New onset Diabetes Mellitus SMQ)

Hypersensitivity (Selected PTs)

LRTI Excluding Pneumonia (Selected PTs)

Local Steroid Effects (Selected PTs)

Ocular effects including the following subgroups:

- Glaucoma (SMQ)
- Lens Disorders (SMQ)

Pneumonia (Selected PTs)

Tremor (Selected PTs)

If this reference data is updated between the RAP being approved and the reporting of the study, then this list will be updated and re-reviewed. A listing of all preferred terms used to identify AESIs will be produced.

#### Rate of Adverse Events per 100 Treatment Years

Rate of on-treatment adverse events per 100 treatment years will be calculated using:

Rate = number of events \* 100 / total treatment exposure in years

#### Rate of Adverse Events per 100 Treatment Years

where subjects can contribute more than one event.

This is equivalent to:

Rate = number of events \* 100 / (number of subjects in treatment group \* mean treatment exposure in vears).

Note: The rate must be produced to sufficient decimal places to allow the conversion to rate of adverse events per 1000 treatment years if required. Exposure will be calculated as defined in Section 9.6.2.

#### Kaplan-Meier Plot of Time to Premature Discontinuation from Investigational Product

Within the Kaplan Meier plot subjects will either be counted as an event or they will be censored.

#### Events:

- Subjects who discontinue investigational product before the end of the study will be counted as an event, with the date of IP discontinuation being used as the treatment end date.
- Subjects who die will be considered as having withdrawn from the IP at the date of death, unless
  they discontinued IP prior to death in which case the IP discontinuation date will be used as
  treatment end date.

#### Censoring:

• Subjects who continue study treatment until the end of the study will be censored at their treatment end date. A subject takes IP for more than 156 weeks will be censored at 156 weeks (1092 days).

Time on investigational product = Treatment end date - Treatment start date + 1

#### Maximum/Minimum On-Treatment Definitions for Vital Signs Data

Maximum and Minimum on-treatment: Maximum and Minimum on-treatment value over all time-points (including scheduled and unscheduled assessments) will be presented.

#### FEV1

#### **Absolute Reversibility**

Absolute reversibility (mL) = (post-bronchodilator FEV1 – pre-bronchodilator FEV1)

#### **Percent Reversibility**

Definition of Percentage Reversibility as a percentage of predicted  $FEV_1 = ((post-bronchodilator FEV_1 - pre-bronchodilator FEV_1) / predicted FEV_1) x 100%$ 

Definition of Percentage Reversibility as a percentage of pre-bronchodilator  $FEV_1$  = ((post-bronchodilator  $FEV_1$ ) / pre-bronchodilator  $FEV_1$ ) x 100%

## 9.7. Appendix 7: Reporting Standards for Missing Data

## 9.7.1. Premature Withdrawals

Element	Reporting Detail	
General	
 
Subject study completion (i.e. as specified in the protocol) was defined as attendance at 13 post-randomisation visits over the schedule.
 
	
	Withdrawn subjects were not replaced in the study	
	Withdrawal visits will be slotted as per Appendix 3: Assessment Windows or will be summarised as withdrawal visits.	

## 9.7.2. Handling of Missing Data

Element	Reporting Detail				
General	
 
Missing data occurs when any requested data is not provided, leading to blank fields on the collection instrument:
 
These data will be indicated by the use of a "blank" in subject listing displays. Unless all data for a specific visit are missing in which case the data is excluded from the table.
 
Answers such as "Not applicable" and "Not evaluable" are not considered to be missing data and should be displayed as such.
 
				

## 9.7.2.1. Handling of Missing and Partial Dates

Element	Reporting Detail
General	Partial dates will be displayed as captured in subject listing displays.
Adverse Events	
 
The eCRF allows for the possibility of partial dates (i.e., only month and year) to be recorded for AE start and end dates; that is, the day of the month may be missing.
 
Any partial dates for adverse events will be raised to data management.
 
In such a case, the following conventions will be applied for calculating the time to onset and the duration of the event:         
 
Missing Start Day: First of the month will be used
 
Missing Stop Day: Last day of the month will be used, unless the subject died and this date is after the subject's death date in which case the stop date will be set to the death date
 
 
 
Completely missing start or end dates will remain missing, with no imputation applied. Consequently, time to onset and duration of such events will be missing.
 

Concomitant Medications	
 
Partial dates for any concomitant medications recorded in the CRF will be imputed using the following convention:         
 
If the partial date is a start date, a '01' will be used for the day and 'Jan' will be used for the month
 
If the partial date is a stop date, a '28/29/30/31' will be used for the day (dependent on the month and year) and 'Dec' will be used for the month. If this imputed stop date is after the subject death date then the stop date will be set to the death date.
 
 
 
The recorded partial date will be displayed in listings.         
 
Completely missing start or end dates will remain missing, with no imputation applied.
 
 
 

Protocol Devaiations	
 
The eCRF allows for the possibility of partial dates (i.e., only month and year) to be recorded for protocol deviation dates; that is, the day of the month may be missing.
 
In this case the first day of the month will be used. This is to allow the protocol deviation to have occurred at the earliest possible date.
 

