Dispense Single-Blind Medication		Х															
Dispense Double- Blind Medication			Х	Х	Х	Х	Х	Х	Х	Х	Х	Х	Х	Х			
Collect Blinded Medication			Х	Х	Х	Х	Х	Х	Х	Х	Х	Х	Х	Х	Х	Х	
Other Assessment																	

2012N150072_01

CONFIDENTIAL

2018N368712_00 HZC102972

Double-Blind Treatment period 2 3 15 0 1 4 5 6 7 8 9 10 11 12 13 14 Random-Pre-Screen-Early Follow Visit Number screen1 ing² ization With--up draw 13 26 39 52 65 78 91 104 117 130 143 156 Visit Day 1 wks 14/EW ± 14 ± 14 ±14 ± 14 ± 14 ± 14 ±14 + 7±2 ± 14 ± 14 ± 14 ± 14 ± 14 Days Days Days Davs Days Days Days Davs Days Days Days Days Days Discharge from Х Х Study¹⁵

1. Visit 0 and Visit 1 may occur on the same day if the subject does not take or has not taken any protocol excluded medications.

- 2. Following Screening Visit 1, subjects enter a 14 to 21 day single-blind run-in period.
- 3. Subjects will be assigned a subject number at the time ICF is signed. The ICF must be signed before any study procedures including medication exclusion period(s).
- 4. Saliva (2ml) sample is collected in the DNA self-collection kit. This should ideally be taken as soon after randomization (Visit 2) as possible, but may be taken at any other visit after randomization if necessary. PGx consent must be signed prior to PGx sampling.
- 5. A telephone based IVRS system (RAMOS) which will be used by the investigator or designate to register the subject, randomize the subject and provide medication assignment information.
- 6. Baseline BMD measurements will be collected between Visit 1 and Visit 2.
- 7. If evidence of infection, culture swab may be taken and appropriate therapy should be instituted at Investigator discretion. Subjects with culture-positive infection may continue in the study on appropriate anti-infective treatment at Investigator discretion.
- 8. Chest X-ray must be taken if a Chest X-ray or CT scan is not available within the 12 months preceding Visit 1. Chest x-rays will be requested for suspected cases of pneumonia.
- 9. Non-fasting and pre-dose. A blood sample for repeat analysis is collected only if any part of Screening lab needs to be repeated. Results of repeat labs should be received prior to Randomization at Visit 2.
- 10. Females of child-bearing potential only
- 11. Adverse events are to be collected from the start of blinded study medication (Visit 2) until the follow-up phone contact.

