# 9.4. Appendix 4: Study Phases and Treatment Emergent Adverse Events

Subjects who do not take study treatment who have will have events, log recordings and measurements assigned to pre-treatment.

Events, log recordings and measurements with missing dates will be assigned to ontreatment for subjects who have taken study treatment, unless there is evidence it was not on-treatment.

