# 9.4.3. Study Phases for Adverse Events and All Other Data Recorded in Logs (excluding Concomitant Medications)

Study Phase	Definition
Pre-Treatment	Event Onset Date < Study Treatment Start Date
On-Treatment	Study Treatment Start Date ≤ Event Onset Date ≤ Study Treatment Stop Date + 1
Post-Treatment	Event Onset Date > Study Treatment Stop Date + 1

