# 9.4.5. Treatment Emergent Flag for Adverse Events, Pneumonia and Exacerbations

Flag	Definition
Treatment Emergent	
 
If AE onset date is on or after treatment start date & on or before treatment stop date plus one day.
 
Study Treatment Start Date ≤ AE Start Date ≤ Study Treatment Stop Date + 1.
 

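### The SAP imputes a missing AE start day to the 1st of the month with no floor at first dose, giving impossible negative onset times, and does not say which date sets study phase for partly dated events

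*SAP*

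**What the plan says.** SAP 9.7.2.1 allows an AE date to be recorded as month and year only. Such dates go first to a query step: "Any partial dates for adverse events will be raised to data management". For those that stay partial, "the following conventions will be applied for calculating the time to onset and the duration of the event", and the start-date convention is "Missing Start Day: First of the month will be used". An imputed stop day is capped at the date of death; the imputed start day has no bound. A wholly missing start date is left missing.

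Study phase is set in SAP Appendix 4. Its opening text (9.4) reads: "Events, log recordings and measurements with missing dates will be assigned to ontreatment for subjects who have taken study treatment", unless there is evidence to the contrary. Section 9.4.3 makes an AE pre-treatment when "Event Onset Date < Study Treatment Start Date", and 9.4.5 sets the treatment-emergent flag when "Study Treatment Start Date ≤ AE Start Date ≤ Study Treatment Stop Date + 1". Neither AE section refers to 9.7.2.1. The notes to the concomitant-medication phases in 9.4.4 do.

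On collection, footnote 11 to Table 3 of the protocol says: "Adverse events are to be collected from the start of blinded study medication (Visit 2) until the follow-up phone contact". Protocol 6.2.8 and 6.2.13 agree. The exception is a serious adverse event (SAE) related to study participation or to a sponsor concomitant medication, which is recorded from consent (footnote 12 and 6.2.13).

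**The concern.** The imputation rule and the collection rule do not fit together. If non-serious AEs are recorded only from first dose, such an AE dated to the first-dose month must have begun on or after first dose. Moving its onset to the 1st puts it before treatment for almost every subject, in conflict with what the trial knows about the event.

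Two things are at stake. The first is the time to onset, which is the stated purpose of the convention and comes out negative. The second is the count of on-treatment events. If the same imputed date is compared with treatment start in 9.4.3 and 9.4.5, an event early in treatment is classed as pre-treatment and is not flagged as treatment-emergent. The SAP display list has on-treatment and post-treatment AE tables but no pre-treatment one, although protocol 8.3.5.2.2 planned separate summaries for all three periods.

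**Working it through.** The documents give no figure on this point, so there is none to reproduce. The check applies the SAP's own date rules.

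**Inputs**
- Imputed onset: the 1st of the recorded month (SAP 9.7.2.1).
- Study day for a date before first dose: date minus first-dose date (SAP 9.6.1). The SAP gives no separate formula for AE time to onset, so I use this one.
- Treatment period: 156 × 7 = 1,092 days (SAP 9.6.3).
- Assumptions: first-dose dates spread evenly over a 365-day year (seven months of 31 days, four of 30, one of 28), and onset equally likely on each remaining day of the first-dose month.

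**Step 1. How often the imputed onset precedes first dose.** It does so unless first dose is on the 1st: 365 - 12 = 353 dates, and 353/365 = 96.7%.

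**Step 2. How far before.** For first dose on day d, the study day is 1 - d, which runs from -1 (d = 2) to -30 (d = 31). In a month of L days the total displacement is L(L - 1)/2. Over the year: 7 × 465 + 4 × 435 + 378 = 5,373 days. The mean study day is -5,373/353 = -15.2.

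**Step 3. How much treatment time is exposed.** From first dose to month end there are L - d + 1 days, totalling L(L + 1)/2 per month. Over the year: 7 × 496 + 4 × 465 + 406 = 5,738. The mean is 5,738/365 = 15.7 days, and 15.7/1,092 = 1.4% of the treatment period. Within that window, the imputed date precedes first dose for 5,373/5,738 = 94% of possible onset days.

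**Step 4. Example.** First dose 15 March, AE recorded as March. The rule gives 1 March, study day -14. With a floor at treatment start it gives 15 March, study day 1.

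**Step 5. Which date sets the phase.** Two readings are open:
- A partial date counts as a missing date under 9.4. The event is on-treatment and only the onset time is wrong.
- A partial date is not a missing date, because 9.7.2.1 treats partial and wholly missing dates differently. The only full date available is then the 1st, and 9.4.3 classes the event as pre-treatment.

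Under the second reading the event drops out of the tables limited to on-treatment AEs, for example 2.30 (all AEs, with rates), 2.36 (drug-related AEs), and 2.47 and 2.48 (AEs of special interest). By title it stays within the scope of Table 2.40, if its term reaches 3%, or of Table 2.42 if it is serious. It also stays in Listing 11 (all AEs) and, if serious, Listing 14.

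**The case against.** The strongest reply is that the SAP never tells anyone to use the imputed date for phase. The convention is limited to onset time and duration. Phase has its own appendix with an on-treatment default. Where the authors wanted partial-date imputation to feed phase, for concomitant medications, they wrote the cross-reference. The collection window also supports on-treatment assignment. This stands as far as it goes: a reader might infer that these events are filed as pre-treatment by rule, and the text does not say that. It does not say the opposite either, because the 9.4 default speaks of missing dates and 9.7.2.1 separates those from partial ones. Two programmers could reach different answers.

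A second reply is that the negative onset time reaches no named output. No AE table or figure has time to onset in its title, and AE rates use event counts and total exposure. That is correct, but the mock shells are not included, so a listing column cannot be ruled out. The value is wrong wherever it appears.

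A third reply is that a plain floor would create its own error. Run-in lasts 14 to 21 days and can share a calendar month with first dose, so a study-related SAE from run-in with a partial date would be moved to first dose and become on-treatment. This stands, and the fix needs an exception for it.

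**Conclusion.** One part is definite: the stated rule has no floor at treatment start, and for a non-serious AE dated only to the first-dose month it produces an impossible negative time to onset for 96.7% of first-dose dates. The other part is an ambiguity: the SAP does not say which date drives 9.4.3 and 9.4.5 for a partial AE date. Misclassification is possible but not mandated.

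Two stronger conclusions are tempting and are not supported. One is that the events appear in no AE table; the titles of Tables 2.40 and 2.42, and the listings, carry no phase limit. The other is that the error always lowers on-treatment counts. If the imputed date drives phase, it can only lower them in the first-dose month, but in the month of last dose the same rule can move a post-treatment event into the on-treatment period.

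The effect is small. The 96.7% is a share of first-dose dates, not of subjects or events. An event is affected only if it falls in the first-dose month, about 1.4% of treatment time under even spread, and its day is still unknown after query. The documents do not give the share of AE dates that stay partial, so the number of events cannot be computed. Nothing in the documents points to a difference between the blinded arms. This is a worthwhile correction, not a threat to the trial's conclusions.

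**What to change.** Amend SAP 9.7.2.1: when the partial month and year match those of first dose, set onset to the later of the 1st and the treatment start date, unless there is evidence that onset preceded first dose (for example, a study-related SAE recorded during run-in); otherwise use the 1st.

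Add to 9.4.3 and 9.4.5 that this same date determines study phase and the treatment-emergent flag. Apply the rule to fracture, pneumonia and exacerbation onset dates if those forms allow partial dates; 9.7.2.1 currently names only AEs, concomitant medications and protocol deviations.

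The cost is about two sentences in the SAP and one line of code, to be settled before unblinding.

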# 9.8. Appendix 11: Abbreviations & Trade Marks

## 9.8.1. Abbreviations

Abbreviation	Description
ADaM	Analysis Data Model
AE	Adverse Event
A&R	Analysis and Reporting
CDISC	Clinical Data Interchange Standards Consortium
CI	Confidence Interval
CS	Clinical Statistics
CSR	Clinical Study Report
CV b /CV w	Coefficient of Variation (Between) / Coefficient of Variation (Within)
DOB	Date of Birth
DP	Decimal Places
eCRF	Electronic Case Record Form
FF/VI	Fluticasone Furoate/ Vilanterol Inhalation Powder Combination
GCSP	Global Clinical Safety Pharmacovigilance
GSK	GlaxoSmithKline
ICH	International Conference on Harmonisation
IDSL	Integrated Data Standards Library
IMMS	International Modules Management System
IP	Investigational Product
ITT	Intent-To-Treat
GUI	Guidance
LRTI	Lower Respiratory Tract Infection
MMRM	Mixed Model Repeated Measures
PCI	Potential Clinical Importance
PDMP	Protocol Deviation Management Plan
PP	Per Protocol
QC	Quality Control
QTcF	Frederica's QT Interval Corrected for Heart Rate
QTcB	Bazett's QT Interval Corrected for Heart Rate
RAP	Reporting & Analysis Plan
RAMOS	Randomisation & Medication Ordering System
SAC	Statistical Analysis Complete
SDTM	Study Data Tabulation Model
SOP	Standard Operation Procedure
TA	Therapeutic Area
TFL	Tables, Figures & Listings
VI	Vilanterol Inhalation Powder

## 9.8.2. Trademarks

Trademarks of the GlaxoSmithKline Group of Companies

ELLIPTA

Trademarks not owned by the GlaxoSmithKline Group of Companies

HARP

### 9.9. Appendix 12: List of Data Displays

### 9.9.1. Data Display Numbering

The following numbering will be applied for RAP generated displays:

Section	Tables	Figures	
Study Population	1.001 to 1.XXX	1.001 to 1.XXX	
Safety	2.001 to 2.XXX 2.001 to 2.XXX		
Section	Listings		
ICH Listings	1 to XX		
Other Listings	XX to	o YY	

## 9.9.2. Mock Example Shell Referencing

Non IDSL specifications will be referenced as indicated and if required an example mock-up displays provided in Appendix 13 15: Example Mock Shells for Data Displays.

Section	Figure	Table	Listing
Study Population	POP_F	POP_T	POP_L
Safety	SAFE_F	SAFE_T	SAFE_L

#### NOTES:

Non-Standard displays are indicated in the 'IDSL / TST ID / Example Shell' or 'Programming Notes' column as '[Non-Standard] + Reference.'

## 9.9.3. Deliverable [Priority]

Delivery [Priority] [1]	Description
SAC [1]	Final Statistical Analysis Complete

#### NOTES:

1. Indicates priority (i.e. order) in which displays will be generated for the reporting effort.

# 9.9.4. Study Population Tables

Study	Study Population Tables					
No.	Population	IDSL / Example Shell	Title	Programming Notes	Deliverable [Priority]	
Subjec	t Disposition					
1.1.	Enrolled	SP1	Summary of Study Populations	IDSL	SAC [1]	
1.2.	SAF	ES1	Summary of Subjects Disposition for the Subjects Conclusion Record	ICH E3, FDAAA, EudraCT	SAC [1]	
1.3.	SRIF	ES6	Summary of Pre-screening, Screening and Run-in Status and Reasons for Screen and Run-in Failure	Journal Requirements, Page by Screening and Run-in	SAC [1]	
1.4.	Enrolled	NS1	Summary of Number of Subjects Enrolled by Country and Site ID	EudraCT/Clinical Operations	SAC [1]	
1.5.	SAF	SP2	Summary of Attendance at Each Clinic Visit		SAC [1]	
Protoc	ol Deviation					
1.6.	SAF	DV1	Summary of Important Protocol Deviations	ICH E3	SAC [1]	
1.7.	SAF	IE1	Summary of Inclusion/ Exclusion Deviations		SAC [1]	
1.8.	Screened	IE2	Summary of Failed Inclusion/ Exclusion Criteria	Include 'Number of Screen or Run-in Failures' row at the top of the table. This is to be used as the denominator for the % calculations.	SAC [1]	
Demog	raphic and Bas	seline Characteris	tics			
1.9.	SAF	DM1	Summary of Demographic Characteristics	ICH E3, FDAAA, EudraCT	SAC [1]	
1.10.	SAF	DM1	Summary of Demographic Characteristics by Country		SAC [1]	
1.11.	Enrolled	DM11	Summary of Age Ranges	EudraCT	SAC [1]	
1.12.	SAF	DM5	Summary of Race and Racial Combinations	ICH E3, FDA, FDAAA, EudraCT	SAC [1]	
1.13.	SAF	DM6	Summary of Race and Racial Combination Details		SAC [1]	

Study	Study Population Tables					
No.	Population	IDSL / Example Shell	Title	Programming Notes	Deliverable [Priority]	
Prior a	nd Concomitan	t Medications				
1.14.	SAF	MH4	Summary of Current Medical Conditions	ICH E3	SAC [1]	
1.15.	SAF	MH4	Summary of Past Medical Conditions	ICH E3	SAC [1]	
1.16.	SAF	POP_T01	Summary of Cardiovascular History/Risk Factors		SAC [1]	
1.17.	SAF	SP07	Summary of Family History of Cardiovascular Risk Factors at Screening		SAC [1]	
1.18.	SAF	POP_T02	Summary of Disease Duration	ICH E3	SAC [1]	
1.19.	SAF	CM1	Summary of Pre-treatment COPD Medications	ICH E3	SAC [1]	
1.20.	SAF	CM1	Summary of On-treatment COPD Concomitant Medications	ICH E3	SAC [1]	
1.21.	SAF	SP11	Summary of On-treatment Concomitant Medications Not Given for a COPD Exacerbation	ICH E3	SAC [1]	
1.22.	SAF	SP11	Summary of On-treatment Concomitant Medications Given for a COPD Exacerbation	ICH E3	SAC [1]	
1.23.	SAF	CM1	Summary of Post-treatment COPD Medications	ICH E3	SAC [1]	
1.24.	SAF	CM1	Summary of On-treatment BMD Concomitant Medications	ICH E3	SAC [1]	
1.25.	SAF	CM1	Summary of Post-treatment BMD Medications	ICH E3	SAC [1]	
1.26.	SAF	CM1	Summary of On-treatment Other Concomitant Medications	ICH E3. Other concomitant mediations are all non-BMD and non-COPD medications.	SAC [1]	
1.27.	SAF	CM1	Summary of Post-treatment Other Medications	ICH E3	SAC [1]	
1.28.	SAF	SU1	Summary of Smoking History at Screening		SAC [1]	
1.29.	SAF		Summary of Baseline Bone Mineral Density Test Results		SAC [1]	

Study F	Study Population Tables					
No.	Population	IDSL / Example Shell	Title	Programming Notes	Deliverable [Priority]	
Baselin	e Spirometry					
1.30.	SAF	SP12	Summary of Lung Function Test Results at Screening and Randomisation	Include Pre- and Post- albuterol (salbutamol) FEV 1 , FVC, FEV 1 /FVC and % Predicted Normal and post-BD at screening %predicted. Page by visit. Include overall and by treatment group.	SAC [1]	
Treatmo	Treatment Compliance					
1.31.	SAF	SP6	Summary of Treatment Compliance	ICH E3	SAC [1]	

